**Table 1-10 Primary, secondary and exploratory variables**

| Variable   | Type        |
|--|-------------|
| Long term safety and tolerability of secukinumab             | Primary     |
| Maintenance of response                                      | Secondary   |
| PASI 50/75/90/100 and IGA mod 2011 0 or 1 response over time | Secondary   |
| PASI score over time   | Secondary   |
| IGA mod 2011 score over time                                 | Secondary   |
| Start of relapse   | Secondary   |
| Time to relapse  | Secondary   |
| Rebound  | Secondary   |
| DLQI 0 or 1 achievement                                      | Secondary   |
| EQ-5D  | Secondary   |
| DLQI   | Secondary   |
| HAQ-DI score over time                                       | Exploratory |

| Variable                               | Type        |
|--|-------------|
| HAQ-DI response over time  | Exploratory |
| [REDACTED]                             | [REDACTED]  |

only for subjects with psoriatic arthritis (PsA) at baseline of core study

### 1.8.1.1 Definition of PASI and related variables

The total BSA affected by plaque-type psoriasis was estimated from the percentages of areas affected, including head, trunk, upper limbs and lower limbs (see below for PASI assessment). The following calculations were done: each reported percentage was multiplied by its respective body region corresponding factor (head = 0.1, trunk = 0.3, upper limbs = 0.2, lower limbs = 0.4). The resulting 4 percentages will be added up to estimate the total BSA affected by plaque-type psoriasis. The PASI scoring system is further described in [Table 1-11](#).

A PASI score ([Fredriksson and Pettersson 1978, Weisman et al 2003, Gottlieb et al 2005](#)) was derived as indicated in [Table 1-11](#). The head, trunk, upper limbs and lower limbs are assessed separately for erythema, thickening (plaque elevation, induration), and scaling (desquamation). The average degree of severity of each sign in each of the four body regions is assigned a score of 0-4. The area covered by lesions on each body region is estimated as a percentage of the total area of that particular body region. Further practical details help the assessment:

1. The neck is assessed as part of the head.
2. The axillae and groin are assessed as part of the trunk.
3. The buttocks are assessed as part of the lower limbs.
4. When scoring the severity of erythema, scales should not be removed.

Because the head and neck, upper limbs, trunk and lower limbs correspond to approximately 10%, 20%, 30% and 40% of the body surface area, respectively, the PASI score was calculated using the formula:

$$\text{PASI} = 0.1 (E_h + I_h + D_h)A_h + 0.2 (E_u + I_u + D_u)A_u + 0.3 (E_t + I_t + D_t)A_t + 0.4 (E_l + I_l + D_l)A_l$$

where E, I, D, and A denote erythema, induration, desquamation, and area, respectively, and h, u, t, and l denote head, upper extremities, trunk, and lower extremities, respectively (see [Table 1-11](#)).

PASI scores can range from a lower value of 0, corresponding to no signs of psoriasis, up to a theoretic maximum of 72.0.

The investigator was only responsible for collecting the components or scoring signs and total regional area. PASI calculations were done via the PASI Score eCRF.

The PASI scores calculated via the PASI Score eCRF will be used in the analysis and for derivation of PASI response values, relapse and rebound (see below).

**Table 1-11 The PASI scoring system**

| Body region     | Erythema (E)  | Thickening (I)
(plaque elevation, induration)                        | Scaling (D)
(desquamation)   | Area score (A)
(based on true area %)*  |
|-----------------|---|---|---|--|
| Head (H)†       | 0 = none
1 = slight
2 = moderate
3 = severe
4 = very severe | 0 = none
1 = slight
2 = moderate
3 = severe
4 = very severe | 0 = none
1 = slight
2 = moderate
3 = severe
4 = very severe | 0 = no involvement
1 = > 0 - < 10
2 = 10 - < 30
3 = 30 - < 50
4 = 50 - < 70
5 = 70 - < 90
6 = 90 - 100 |
| Trunk (T)‡      | 0 = none
1 = slight
2 = moderate
3 = severe
4 = very severe | 0 = none
1 = slight
2 = moderate
3 = severe
4 = very severe | 0 = none
1 = slight
2 = moderate
3 = severe
4 = very severe | 0 = no involvement
1 = > 0 - < 10
2 = 10 - < 30
3 = 30 - < 50
4 = 50 - < 70
5 = 70 - < 90
6 = 90 - 100 |
| Upper limbs (U) | 0 = none
1 = slight
2 = moderate
3 = severe
4 = very severe | 0 = none
1 = slight
2 = moderate
3 = severe
4 = very severe | 0 = none
1 = slight
2 = moderate
3 = severe
4 = very severe | 0 = no involvement
1 = > 0 - < 10
2 = 10 - < 30
3 = 30 - < 50
4 = 50 - < 70
5 = 70 - < 90
6 = 90 - 100 |
| Lower limb (L)§ | 0 = none
1 = slight
2 = moderate
3 = severe
4 = very severe | 0 = none
1 = slight
2 = moderate
3 = severe
4 = very severe | 0 = none
1 = slight
2 = moderate
3 = severe
4 = very severe | 0 = no involvement
1 = > 0 - < 10
2 = 10 - < 30
3 = 30 - < 50
4 = 50 - < 70
5 = 70 - < 90
6 = 90 - 100 |

\* Percentage (not score) of body region (not whole body) affected will be entered in the eCRF

† Neck is assessed as part of the Head (H) body region.

‡ Axillae and groin are assessed as part of the Trunk (T) body region.

§ Buttocks are assessed as part of the Lower limbs (L) body region.

The following definitions are possible efficacy evaluations that can be used in clinical trials in psoriasis ([CHMP/EWP/2454/02, 2004](#)):

- **PASI 50 response:** subjects achieving  $\geq 50\%$  improvement (reduction) in PASI score compared to baseline are defined as PASI 50 responders
- **PASI 75 response:** subjects achieving  $\geq 75\%$  improvement (reduction) in PASI score compared to baseline are defined as PASI 75 responders
- **PASI 90 response:** subjects achieving  $\geq 90\%$  improvement (reduction) in PASI score compared to baseline are defined as PASI 90 responders

- **PASI 100 response:** complete clearing of psoriasis (PASI=0)

**Definition of IGA mod 2011 score and IGA mod 2011 0 or 1 response**

The IGA mod 2011 rating scale for overall psoriatic disease (shown in [Table 1-12](#)) has been developed based on a previous version of the scale used in secukinumab phase II studies, and has been updated in collaboration with health authorities (in particular the FDA). The explanations/descriptions of the points on the scale have been improved to ensure appropriate differentiation between the points.

The IGA mod 2011 used in this study is static, i.e., it refers exclusively to the subject's disease state at the time of the assessments, and does not attempt a comparison with any of the subject's previous disease states, whether at baseline or at a previous visit.

**Table 1-12 The IGA mod 2011 rating scale**

| Score | Short Description | Detailed Description   |
|-------|-------------------|--|
| 0     | Clear             | No signs of psoriasis. Post-inflammatory hyperpigmentation may be present.   |
| 1     | Almost clear      | Normal to pink coloration of lesions; no thickening; no to minimal focal scaling.  |
| 2     | Mild              | Pink to light red coloration; just detectable to mild thickening; predominantly fine scaling.                                      |
| 3     | Moderate          | Dull bright red, clearly distinguishable erythema; clearly distinguishable to moderate thickening; moderate scaling.               |
| 4     | Severe            | Bright to deep dark red coloration; severe thickening with hard edges; severe / coarse scaling covering almost all or all lesions. |

Note: Involvement of nails is not part of the assessment.

Based on this scale, subjects will be considered as **IGA mod 2011 0 or 1 responder** if they achieve a score of 0 or 1 and improve by at least 2 points on the IGA scale compared to baseline.

**1.8.1.2 Health Assessment Questionnaire - Disability Index (HAQ-DI)**

The Health Assessment Questionnaire (HAQ©) was developed by Stanford University and is one of the most widely used measures to assess the long-term influence of chronic disease on a subject's level of functional ability and activity restriction. The disability assessment component of the HAQ (Health Assessment Questionnaire – Disability Index), the HAQ-DI, assesses a subject's level of functional ability and includes questions of fine movements of the upper extremity, locomotor activities of the lower extremity, and activities that involve both upper and lower extremities. There are 20 questions in eight categories of functioning including dressing, rising, eating, walking, hygiene, reach, grip, and usual activities. The stem of each item asks over the past week "Are you able to ..." perform a particular task. Each item is scored on a 4-point scale from 0 to 3, representing normal (normal, no difficulty [0]), some difficulty [1], much difficulty [2], and unable to do [3].

Scoring for the eight functional categories and overall disability index scoring will be performed as follows:

There are eight categories; first score within each category:

- Dressing and Grooming, includes items 1 and 2
- Arising, includes items 3 and 4
- Eating, includes items 5, 6 and 7
- Walking, includes items 8 and 9
- Hygiene, includes items 10, 11, and 12
- Reach, includes items 13 and 14
- Grip, includes items 15, 16 and 17
- Activities, includes items 18, 19, and 20

The score for each category will be the single response within the category with the highest score (greatest difficulty). For example, in the "Eating" category, there are two answers (one for each item). If "Cut your food with a knife or fork" is marked as "3" and "Lift a full cup or glass to your mouth" is marked as "0", then the score for the "Eating" category would be "3" (the response indicating the greatest difficulty within the category). If a component question is left blank or the response is too ambiguous to assign a score, then the score for that category will be determined by the remaining completed question(s). However, if any "aids or devices" and/or "help from another person" items at the bottom of each page are checked with the exception of "other", the category to which they apply will be adjusted upward to "2". If the basic score is already "2" or "3", the score remains unchanged. "Aids or devices" and "help from another person" can only change a category's score to "2"; they do not change the score to a "1" or a "3". Companion aids/devices items for HAQ-DI categories are presented in [Table 1-13](#). No score will be adjusted for "other" ticked, regardless of the "other" specification.

The score for the disability index will be the mean of the eight category scores. If more than two of the categories, or 25%, are missing, scale will not be scored. If fewer than 2 of the categories are missing, divide the sum of the categories by the number of answered categories. The higher score indicates greater disability.

HAQ-DI response is defined by an improvement of at least 0.3 score points compared to baseline.

**Table 1-13 Companion aids/devices items for HAQ-DI categories**

| HAQ-DI Category     | Companion Item   |
|---------------------|--|
| Dressing & Grooming | Devices used for dressing (button hook, zipper pull, long handled shoe horn etc.)    |
| Arising             | Built up or special chair  |
| Eating              | Built up or special utensils   |
| Walking             | Cane walker, crutches  |
| Hygiene             | Raised toilet seat, bathtub seat, bathtub bar
Long handled appliances in bathroom |
| Reach               | Long handled appliances for reach  |
| Grip                | Jar opener (for jars previously opened)  |

**1.8.1.3 Overview of analysis methods of efficacy variables**

An overview of statistical analyses and methods applied to psoriasis efficacy variables is given in [Table 1-14](#)

**Table 1-14 Overview of analysis methods for efficacy variables**

| Variable(s)                                 | Summary statistics for binary/ categorical data | Summary statistics for continuous data | Graphs |
|---|---|--|--------|
| Maintenance of response                     | X   |  |        |
| PASI 50/75/90/100 response over time        | X   |  | X      |
| <hr/>                                       |   |  |        |
| Absolute PASI score over time               |   | X                                      |        |
| Absolute change and % change PASI over time |   | X                                      |        |
| IGA mod 2011 0 or 1 response over time      | X   |  | X      |
| IGA mod 2011 score over time                |   | X                                      |        |
| Relapse                                     | X   |  |        |
| Rebound                                     | X   |  |        |
| EQ-5D                                       | X   | X                                      |        |
| Absolute DLQI                               |   | X                                      |        |
| % change DLQI                               |   | X                                      |        |
| DLQI 0 or 1 achievement                     | X   |  |        |
| HAQ-DI score over time                      |   | X                          |        |
| HAQ-DI response over time                   | X                                   |  |        |

only for subjects with psoriatic arthritis (PsA) at baseline of core study

### **1.8.2 Statistical hypothesis, model, and method of analysis**

Not applicable.

### **1.8.3 Testing strategy**

No formal hypothesis testing will be performed for this extension study.

### **1.8.4 Handling of missing values/censoring/discontinuations**

As observed value (Follow-up assessment excluded) will be reported primarily for both efficacy and PROs.

Response variables based on PASI score and IGA mod 2011 categories will be imputed with multiple imputation (MI) (Follow-up assessment excluded) as secondary analysis method. Summary tables for PASI scores and IGA mod 2011 categories will also be imputed using MI. Other response variables (e.g. DLQI 0 or 1 achievement) will be imputed with LOCF (Follow-up assessment excluded).

#### **1.8.4.1 Multiple imputations for response**

The number of imputations will be set to 100 the seed for the random function will be set to 4572304 for this study.

Multiple imputation (MI) is a simulation based approach where missing values are replaced by multiple Bayesian draws from the conditional distribution of missing data given the observed data and covariates, creating multiple completed data sets. These completed data sets can then be analyzed using standard methods. Within this analysis the PASI score change from baseline or IGA mod 2011 categories will be imputed separately and response variables will be derived based on the imputed scores. In the multiple imputation analysis the response status will be imputed based on the individual treatment arm information.

Of note: subjects with missing baseline or subjects with all post-baseline missing will be included in the multiple imputation analysis.

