3.3 Rationale of dose/regimen, route of administration and duration of treatment

The doses and regimens selected for the secukinumab phase III program were based on phase II trial data. As of the trial initiation, there has not been any data to date to indicate that the doses used in the core studies should be modified. Therefore, this extension study will continue treatment with secukinumab s.c. doses of 150 mg and 300 mg administered every four weeks, and/or at start of relapse (following the randomization that was done during the core studies) for an additional 208 weeks. This will provide long-term secukinumab efficacy and safety data pertaining to the treatment of subjects suffering from chronic plaque-type psoriasis for up to a total of 5 years when combined with the core studies data.

The pivotal phase III trials were analyzed while this extension trial was ongoing and results of protocol CAIN457A2304 showed that the re-treatment at start of relapse maintenance regimen (SoR) was not non-inferior to a fixed interval regimen (FI) with treatment every four weeks and subjects experience better efficacy with 300 mg secukinumab s.c. every four weeks compared to 150 mg secukinumab s.c. every four weeks with similar safety profile between the two doses. Therefore, at Week 156 all patients treated with the SoR treatment regimen are given the option to switch to treatment with active secukinumab every four weeks, and patients treated with secukinumab 150 mg s.c. are given the option to switch to treatment with secukinumab 300 mg s.c. Any switches in treatment regimen or dose are to be made according to the investigator's judgment as the investigator will have three years of experience with the subject and the subject's individual response to secukinumab.

The switch from the lyophilisate to the more convenient prefilled syringe (PFS) is supported by the results of the clinical study CAIN457A2106, which has shown that the exposure and safety profiles of both formulations are highly comparable.

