## 1.2 Subjects and treatments

The following analysis sets will be used for the data analysis.

**Extension Full analysis set (FAS):** The FAS will be comprised of all subjects from the randomized set to whom study treatments has been assigned and entered the extension study. Following the intent-to-treat principle, subjects will be analyzed according to the treatment assigned to at randomization in A2304 and A2307 and thereafter reassigned to treatment at Week 156. If the actual stratum is different to the assigned stratum in IRT, the actual stratum will be used in analyses.

Of note, subjects excluded from the randomized set will be excluded from the FAS.

**Extension Safety set:** The safety set includes all subjects who took at least one dose of study treatment during the extension treatment period. Subjects will be analyzed according to treatment received. The treatment received will be set to the treatment randomized. But if a subject has received the wrong treatment during the entire study, the treatment received will be set to this wrong treatment.

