**Retreatment at start of relapse regimen – “SOR”: “start of relapse” either 150 or 300 mg s.c. secukinumab:** “Start of relapse” will be defined as a loss of  $\geq 20\%$  of the maximum PASI gain achieved during the study compared to baseline, *and* a loss of PASI 75 response. Whenever a subject fulfills the start of relapse criteria, active secukinumab will be administered at their scheduled visits (i.e. every four weeks) until the subject is back to PASI 75 response. The dose administered in the maintenance period (secukinumab 150 mg or 300 mg) will be identical to the dose that these subjects received during the induction period. If a subject does not fulfill the criteria of a start of relapse or is back to PASI 75 response after a start of relapse, they will receive placebo injections (two injections per dose) to maintain the blind. This treatment regimen is applied every four weeks, from week 12 up to and including week 48.

**Open label (OL) 300 mg s.c. secukinumab:** All the partial responders at week 12 in induction period in A2304 will enter A2307 double blind i.v. period (for 8 weeks) and these subjects will be randomized with 1:1 ratio into either “300 mg s.c. secukinumab” or “10 mg per kg i.v. secukinumab”. All the subjects will enter open label 300 mg s.c. secukinumab maintenance period from week 8 to week 40.

All the subjects who are eligible from the above 5 treatment groups (4 treatment groups from A2304 and 1 treatment group from A2307) enter the A2304E1 extension study treatment period and continue with same treatment groups. At Week 156, patients under AIN457 150mg FI arm, AIN457 150mg SOR arm, and AIN457 300mg SOR arm could be switched to AIN457 300mg FI arm as determined by physician’s judgement.

For the final analysis, data will be presented for the following treatment groups:

- AIN457 150 mg FI
- AIN457 150 mg FI switch to AIN457 300mg FI
- AIN457 150 mg FI combined non-switch and switch
- AIN457 300 mg FI
- AIN457 150 mg SoR non-switched
- AIN457 150mg SoR switch to AIN457 300mg FI
- AIN457 300 mg SoR non-switched
- AIN457 300mg SoR switch to AIN457 300mg FI
- AIN457 300 mg OL
- Any AIN457 300mg
- Any AIN457 150mg
- Any AIN457

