#### 2.2.2 Multiple imputations for response variables

In the multiple imputations analysis the response status will be imputed based on the individual treatment arm information.

In case of higher drop-out rates or higher study treatment discontinuations for reasons other than lack of efficacy additional sensitivity analyses will be performed.

Multiple imputation (MI) is a simulation based approach where missing values are replaced by multiple Bayesian draws from the conditional distribution of missing data given the observed data and covariates, creating multiple completed data sets. These completed data sets can then be analyzed using standard methods. [Rubin \(1987\)](#) presented rules how to combine the multiple sets of estimates to produce overall estimates and confidence intervals that adequately incorporate missing data uncertainty.

Missing values for the ‘change from baseline PASI score’ and ‘IGA mod 2011 score’ will be imputed simultaneously based on an underlying joint normal distribution and using a Markov Chain Monte Carlo (MCMC) method. The change from baseline in PASI score appears to follow closer to a normal distribution than the actual PASI score. Assuming normality for the ‘IGA mod 2011 score’ is motivated by [Schaefer \(1997\)](#), where it was shown that the multivariate normal approximation for the imputation of incomplete categorical and binary data is robust.

The imputations will be done separately for each treatment group including baseline weight, failure to at least one previous biologic (yes/no), and number of previous systemic therapies as additional covariates.

The number of imputations will be set to 100, the seed for the random function will be set to 4572304 for this study. To generate the multiple imputed data sets, the SAS procedure MI can be used as follows:

The input data set <pasi\_in> should have one record per subject with baseline PASI score and IGA mod 2011 score as well as all changes from baseline PASI and post-baseline IGA mod 2011 score.

```
ODS LISTING CLOSE;
ODS OUTPUT MissPattern=msgpat VarianceInfo=varinfo ParameterEstimates=param;
PROC MI DATA=<pasi_in> OUT=<impdata> SEED=457<studycode> NIMPUTE=100;
  VAR <baseline weight> <failure to at least one biologic>
      <number of previous systemic therapies>
      <baseline PASI>
      <change from baseline PASI week 1> - <change from baseline PASI week primary endpoint>;
  BY <treatment group>;
RUN;
ODS LISTING;
```

Programming notes:

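### Multiple imputation by treatment groups that are split at the Week 156 switch may bias the non-switched response rates; impute by the arm held up to Week 156

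*SAP*

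**What the plan says.** SAP 1.8.4.1: "In the multiple imputation analysis the response status will be imputed based on the individual treatment arm information". SAP 2.2.2: "The imputations will be done separately for each treatment group including baseline weight" and further covariates. The PROC MI template there carries the statement "BY <treatment group>". Its variable list includes "<change from baseline PASI week 1> - <change from baseline PASI week primary endpoint>", so each subject's own PASI course enters the model. No variable identifies the arm held before Week 156.

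SAP 1.2 lists the final-analysis groups. 150 mg FI, 150 mg SoR and 300 mg SoR each appear as a switched and a non-switched group, for example "AIN457 150 mg SoR non-switched". One pooled column is listed for such an arm, "AIN457 150 mg FI combined non-switch and switch". Table 1-2 applies the split groups to maintenance of response and to PASI and IGA over time. It applies the pooled 150 mg FI column to the latter but not to maintenance of response. SoR has no pooled column.

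The FAS definition in SAP 1.2 analyses subjects as assigned at randomization "and thereafter reassigned to treatment at Week 156". It is silent on subjects who left earlier.

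On who switches, Protocol 3.3 says "Any switches in treatment regimen or dose are to be made according to the" investigator's judgment, and justifies this by three years' experience of the subject, including the individual response. Protocol 5.3 and Table 5-1 set no response threshold.

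**The concern.** If the BY groups are the listed final groups, imputation is stratified on a decision taken after the early leavers had gone. They cannot belong to a switched group, so the non-switched group is the only listed single group left for them. The model that fills in their later visits is then fitted without those subjects of the same arm who were switched. Even if data are missing at random within the assigned arm, that need not hold within a subset chosen by a later decision that may depend on response.

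Multiple imputation is the only general method in the SAP that brings drop-outs back into the PASI and IGA results: SAP 1.1.1 drops non-responder imputation for maintenance of response, and SAP 1.8.4 leads with observed values. The first secondary objective compares SoR with FI at the same dose, with Week 156 as one of its two landmarks. In 300 mg FI nobody can switch; in 300 mg SoR they can. Any bias therefore enters only one side of that comparison.

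**Working it through.** **Plan's own figures.** The only arm-level planning figures are in Protocol 9.7. 918 × 0.95 × 0.85 = 741 (stated: about 740). 918 × 0.95 × 0.80 × 0.85 / 4 = 148 per arm (stated: 148). With 148 subjects, 1 − 0.999^148 = 13.8% and 1 − 0.99^148 = 77.4% (stated: 14% and 77%). All reproduce. The documents give no switch rate, no drop-out by arm and no expected imputed rate, so the rest uses assumptions.

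**Weight of early leavers.** With d the proportion leaving before Week 156 and s the proportion of the remainder who switch, their share of a non-switched column is d / [d + (1 − d)(1 − s)]. Amendment 1 of the protocol gives about 108 of 675 discontinued, 16%, pooled over arms and not up to Week 156; 30% is taken as a higher value.

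- d = 0.16, s = 0.3: 0.16 / 0.748 = 21%
- d = 0.16, s = 0.7: 0.16 / 0.412 = 39%
- d = 0.30, s = 0.3: 0.30 / 0.790 = 38%
- d = 0.30, s = 0.7: 0.30 / 0.510 = 59%

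**Simulation.** One arm of 200,000 subjects, nine visits from Week 52 to Week 260, latent normal PASI improvement with a person effect plus AR(1) errors. Drop-out before Week 156 depends on the last observed value. Switching is logistic in the Week 156 value: strongly or moderately more likely in poorer responders, unrelated, or more likely in better responders. Week 52 PASI 75 is 60% or 80%. Normal regression imputation is run (a) within the non-switched column and (b) within the whole arm, with switchers' later values set to missing. Bias is the imputed rate minus the true on-regimen rate of the same subjects.

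Week 156 results with Week 52 PASI 75 of 80% (%, biases in percentage points; differences of rounded entries can be off by 0.1):

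| d / s | Who switches | True | Imputed (a) | Bias (a) | Bias (b) | Observed |
|---|---|---|---|---|---|---|
| 16% / 30% | poorer, strong | 83.5 | 86.0 | +2.5 | 0.0 | 90.1 |
| 16% / 30% | poorer, moderate | 77.0 | 77.8 | +0.8 | 0.0 | 81.8 |
| 16% / 30% | unrelated | 71.8 | 71.7 | −0.1 | 0.0 | 75.3 |
| 16% / 30% | better | 67.5 | 66.9 | −0.7 | 0.0 | 69.8 |
| 30% / 70% | poorer, strong | 76.3 | 87.7 | +11.4 | −0.1 | 98.2 |
| 30% / 70% | poorer, moderate | 72.7 | 76.2 | +3.5 | −0.1 | 89.4 |
| 30% / 70% | unrelated | 67.8 | 66.9 | −0.9 | −0.1 | 77.5 |
| 30% / 70% | better | 61.9 | 57.4 | −4.6 | −0.1 | 63.2 |

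Range of bias (a) over all scenarios:

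| Who switches | Week 104 | Week 156 | Week 208 | Week 260 |
|---|---|---|---|---|
| poorer, moderate | −0.3 to +0.3 | +0.7 to +3.6 | +0.5 to +2.3 | +0.3 to +1.6 |
| poorer, strong | +0.1 to +0.8 | +2.0 to +11.4 | +1.2 to +6.9 | +0.8 to +4.6 |
| unrelated | | −0.9 to −0.1 | | −0.3 to 0.0 |
| better | | −4.7 to −0.7 | | −2.0 to −0.3 |

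Bias (b) stays within about 0.2 points at Weeks 104, 156, 208 and 260 in every scenario.

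**Cross-check.** A simpler simulation used n = 148, 16% drop-out, a true Week 156 rate of 64%, visit correlation 0.5 to 0.7, and switching in 30–70% of responders and 80–95% of non-responders. Early leavers were imputed 10 to 17 points too high. Overall switching is then about 50–80%, so their share is 0.16 / (0.16 + 0.84 × 0.5) = 27.6% to 0.16 / (0.16 + 0.84 × 0.2) = 48.8%. Column bias is roughly 10 × 0.276 = 2.8 to 17 × 0.488 = 8.3 points, inside the range above.

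**The case against.** **The grouping is not settled by the text.** SAP 1.8.4.1 speaks of the individual treatment arm, and SAP 1.2 uses arm for the assigned regimens and also calls the five regimens entering the extension treatment groups. The PROC MI code is a generic template. Imputing by the five assigned arms is a permitted reading. This stands: placing early leavers in a non-switched group is an inference. But the list headed as the final-analysis groups is the split one, so the plainer reading gives the flawed grouping, and the SAP has to exclude it.

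**A reader might infer that the non-switched rates are too high.** The documents do not establish that. The switch option rests on trial-level results as well as individual response, so investigators could switch subjects regardless of response, in which case the bias is close to zero. If better responders switch, the sign reverses.

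**A reader might infer that early leavers are imputed only from subjects who stayed on regimen, or that Week 104 is equally affected.** The model conditions on each subject's own earlier PASI, and early leavers contribute observed data before they leave. Hence the small Week 104 effect.

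**A reader might take 10 to 17 points as the error in the table.** That applies to early leavers only; the column effect in the same setting is about 3 to 8 points.

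**Stakes are limited.** Imputation is secondary to observed values, SAP 1.8.3 excludes formal testing, and a pooled 150 mg FI column exists for PASI and IGA over time. All true. That column helps only if it is imputed as one group, which the SAP does not say, and nothing equivalent exists for SoR or for maintenance of response. The sensitivity analyses mentioned in SAP 2.2.2 have no stated trigger threshold or method.

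**Conclusion.** The point holds as a conditional one. On the plainer reading of SAP 1.2 and 2.2.2, imputation is stratified on a post-drop-out decision, and the non-switched imputed rates for 150 mg FI, 150 mg SoR and 300 mg SoR may be biased at Week 156 and later. Poorer responders switching is the direction that Protocol 3.3 makes most plausible, but it is not certain. In that case the column bias at Week 156 is about +1 to +11 points, shrinking at later visits, and under 1 point at Week 104. These sizes rest on assumed drop-out of 16–30%, switching of 30–70% and an assumed strength of selection.

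300 mg FI and 300 mg open-label have no switch option and are unaffected, so imputed rates are not comparable between regimens. This is so even without imputation bias: with 30% drop-out, 70% switching and no selection, the true rate in the non-switched column is 67.8% against 72.6% for the whole arm, because early leavers are over-represented.

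The observed rate in the non-switched column exceeds the imputed one in every scenario, so reverting to observed values is no remedy. The change should be made; it does not threaten the primary safety objective.

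**What to change.** 1. In SAP 1.8.4.1 and 2.2.2, define the BY variable as the arm held up to Week 156: 150 FI, 300 FI, 150 SoR, 300 SoR, 300 OL. State in SAP 1.2 that subjects who left before Week 156 belong to that arm.
2. Use all subjects' data up to the switch. Protocol 6.4 places efficacy assessments before dosing, so switchers' Week 156 values still describe the earlier regimen. Set their post-switch values to missing for the on-regimen estimate, in line with Protocol 9.4.3, which leaves switchers out of the other efficacy analyses after that point.
3. Report imputed rates by that arm. Add combined switch plus non-switch columns to Table 1-2 for both SoR arms, and for maintenance of response.
4. Form switched and non-switched columns only after imputation, from subjects who reached the Week 156 decision. Label them as selected groups whose rates may exceed the arm estimate. In the simpler simulation, stayers alone showed 86–91% against 83–87% in the mixed column, so this restriction raises the non-switched rate.

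The near-zero bias of this approach in the simulation assumes that drop-out and switching depend on observed values; the SAP should state that assumption.

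Cost: SAP wording, one BY variable and a few added table columns. No new data are needed.
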